### **6.4. Concomitant Therapy**

The use of any concomitant medication, prescription or OTC, is to be recorded on the participant's CRF at each visit along with the reason the medication is taken.

At both visits, site staff will question each participant specifically on the use of concomitant medications. Site staff must notify the sponsor immediately if a participant consumes any concomitant medications not permitted by the protocol. Participants who use(d) prohibited concomitant medications may be discontinued from the study at the discretion of the investigator or the sponsor.

#### **6.4.1. Washout Before the Study**

Contact lens wear must be discontinued at least 7 days prior to the Screening Visit.

#### **6.4.2. Rescue Medicine**

Rescue medicine is not applicable.

#### **6.4.3. Prohibited Interventions During the Study**

The decision to administer a prohibited intervention is done with the safety of the study participant as the primary consideration. When possible, Allergan should be notified before the prohibited intervention is administered. Use of the following interventions is prohibited during the study:

- Contact lens wear within 7 days prior to the Screening Visit
- Punctal or intracanalicular plugs throughout study duration
- Initiation or change in dosing of any ophthalmic cyclosporine preparations (eg, RESTASIS) or lifitegrast 5% ophthalmic solution (Xiidra), any topical ocular glaucoma drop, any topical ocular antihistamine drop, or any artificial tear or lubricant  $\geq$  1 month prior to the Screening Visit, or anticipated change during the study. Drops continuing at stable dosing (defined as having a start date  $\geq$  30 days prior to Screening) may continue to be used. **However, drops should not be used within 2 hours of either study visit.**

#### Intranasal Tear Neurostimulator

- Initiation or anticipated change in dosing of any systemic medication (OTC, herbal, prescription, or nutritional supplements), which may affect dry eye or vision,  $\leq$  1 month prior to the Screening Visit. Such medications may include, but are not limited to, the following: Flax seed oil, fish oil, omega-3 supplements, cyclosporine, antihistamines, cholinergic agents, anticholinergics, antimuscarinics, beta blocking agents, tricyclic antidepressants, phenothiazines, estrogen, progesterone, and other estrogen derivatives.
- Use of lid-heating therapy (ie, LipiFlow, iLUX, etc.), meibomian gland probing, or therapeutic meibomian gland expression in either eye within 3 months prior to the Screening Visit.

#### **6.5. Intervention after the End of the Study**

No interventions after the end of the study are planned.

Intranasal Tear Neurostimulator

## 7. Discontinuation of Study Intervention and Participant Discontinuation/Withdrawal

A premature discontinuation will occur if a participant who signs the ICF and is dosed ceases participation in the study, regardless of circumstances, before the completion of the protocol-defined study procedures.

### 7.1. Study Termination

The study may be stopped at his/her study site at any time by the site investigator. Allergan may stop the study (and/or the study site) for any reason with appropriate notification.

### 7.2. Participant Discontinuation/Withdrawal from the Study

- A participant may withdraw from the study at any time at his/her own request or may be withdrawn at any time at the discretion of the investigator for safety, behavioral, compliance, or administrative reasons.
- Participants will be discontinued if they use any prohibited intervention described in Section 6.4.3.
- For participants who discontinue from the study early, every effort should be made to have these participants return to the clinical center for completion of the exit visit. AEs leading to participant early discontinuation must be followed-up as appropriate.
- If the participant withdraws consent for disclosure of future information, the sponsor may retain and continue to use any data collected before such a withdrawal of consent.
- See the Schedule of Visits and Procedures (Section 1.3) for data to be collected at the time of study discontinuation (early exit).

#### 7.2.1. Reasons for Discontinuation: Acceptable Terms

A premature discontinuation will occur if a participant who signs the ICF and is dosed ceases participation in the study, regardless of circumstances, before the completion of the protocol-defined study procedures.

## Intranasal Tear Neurostimulator

Reasons for discontinuation from the study intervention and/or the study may include the following commonly used or other acceptable terms:

Commonly Used Terms	Other Acceptable Terms
Adverse event	Death
Completed	Failure to meet randomization criteria
Lost to follow-up	Progressive disease
Non-compliance	Recovery
Other	Technical problems
Physician decision	Withdrawal by parent/guardian
Pregnancy	
Protocol deviation	
Screen failure	
Site terminated by sponsor	
Study terminated by sponsor	
Withdrawal by subject	

Intranasal Tear Neurostimulator

## 8. Study Assessments and Procedures

Please see the schedule of activities (Section 1.3) for the Schedule of Visits and Procedures ([Table 1-1](#)). The overall study design is illustrated in [Figure 1-1](#). The visit schedule includes 2 visits: Screening and Application Visits. Study procedures must be performed in sequence as described in the Schedule of Visits and Procedures.

[figure not shown]
- Protocol waivers or exemptions are not allowed.
- Immediate safety concerns should be discussed with the sponsor immediately upon occurrence or awareness to determine if the participant should continue or discontinue study intervention.
- Adherence to the study design requirements, including those specified in the Schedule of Visits and Procedures, is essential and required for study conduct.
- All screening evaluations must be completed and reviewed to confirm that potential participants meet all eligibility criteria. The investigator will maintain a screening log to record details of all participants screened and to confirm eligibility or record reasons for screening failure, as applicable.
- The study will be discussed with the participant and a participant wishing to participate must give informed consent prior to any study-related procedures or change in treatment. The participants must also give authorization and other written documentation in accordance with local privacy requirements (where applicable) prior to any study-related procedures or change in treatment.
- Each participant who provides informed consent will be assigned a participant number that will be used on participant documentation throughout the study.
- WOCBP must have a negative pregnancy test result prior to entry into the study, and prior to ITN device application at the Application Visit.
- A participant is considered to have entered the study at the time of randomization during the Screening Visit (Day -60 to -30). See Section [6.3](#) for the method for assignment to study intervention groups/randomization.

[figure not shown]
Protocol 1919-802-019

[figure not shown]
Intranasal Tear Neurostimulator

**8.1. Visit 1 – Screening (Days -60 to -30)**

**8.2. Visit 2 – Application Visit (Day 0)**

### 8.3. Effectiveness Assessments

Effectiveness assessments are goblet cell degranulation, TMH, and tear film cytokine concentration.

[figure not shown]
Timing and measurement details are provided in [Table 8-1](#).

## Intranasal Tear Neurostimulator

**Table 8–1** Effectiveness Assessments

Assessment	Timing	Measurement
Goblet cell degranulation	

• Screening Visit

• Application Visit after randomized ITN application

	Impression cytology followed by immunofluorescence staining

[figure not shown]
Intranasal Tear Neurostimulator

A large black rectangular box redacting the majority of the page content.

## 8.4. Safety Assessments

### 8.4.1. Corrected Distance Visual Acuity

[figure not shown]
CDVA is performed at the Screening Visit and Application Visit. At the Application Visit, it is performed both prior to and after ITN stimulation. Any changes from baseline should be evaluated for possible reporting as an AE.

A large black rectangular box redacting the majority of the page content.

Protocol 1919-802-019

Intranasal Tear Neurostimulator

Protocol 1919-802-019

Intranasal Tear Neurostimulator

Approval Date: 04-Mar-2019

[figure not shown]
Protocol 1919-802-019

Intranasal Tear Neurostimulator

## **8.5. Other Assessments**

### **8.5.1. Urine Pregnancy Test**

[figure not shown]
WOCBP will have a urine pregnancy test performed at Screening and the Application Visit. Additional details are provided in [Appendix 6](#).

Protocol 1919-802-019

[figure not shown]
Intranasal Tear Neurostimulator

A large black rectangular box redacts the majority of the page content, starting below the header and ending above the page number.

[figure not shown]
[figure not shown]

Protocol 1919-802-019

Intranasal Tear Neurostimulator

## Intranasal Tear Neurostimulator

**8.5.5.     Intranasal Exam (Screening Visit Only)**

The nasal cavity is inspected for vascularized polyp, severely deviated septum, severe nasal airway obstruction, or evidence of prior surgery/cautery. Any other gross abnormalities or irregularities should be documented accordingly.

**8.6.     Adverse Events/Adverse Device Effects and Serious Adverse Events/Serious Adverse Device Effects**

The definitions of an AE/ADE or SAE/SADE can be found in [Appendix 2](#).

AEs/ADEs will be reported by the participant (or, when appropriate, by a caregiver, surrogate, or the participant's legally authorized representative).

The investigator and any qualified designees are responsible for detecting, documenting, and recording events that meet the definition of an AE/ADE or SAE/SADE and remain responsible for following up AEs/ADEs that are serious, considered related to the study intervention or study procedures, or that caused the participant to discontinue the study intervention or study (see Section [7](#)).

## Intranasal Tear Neurostimulator

### **8.6.1. Time Period and Frequency for Collecting Adverse Event/Adverse Device Effect and Serious Adverse Event/Serious Adverse Device Effect Information**

All SAEs/SADEs from the signing of the ICF will be collected at the timepoints specified in the Schedule of Visits and Procedures (Section 1.3), and as observed or reported spontaneously by study participants.

All AEs/ADEs from the signing of the ICF will be collected at the timepoints specified in the Schedule of Visits and Procedures (Section 1.3), and as observed or reported spontaneously by study participants.

Medical occurrences that begin before the start of study intervention, but after obtaining informed consent, will be recorded in the AE section of the CRF.

All SAEs/SADEs will be recorded and reported to the sponsor or designee within 24 hours, as indicated in [Appendix 2](#). The investigator will submit any updated SAE/SADE data to the sponsor within 24 hours of it being available.

The investigator is not obligated to actively seek AE/ADE or SAE/SADE information after conclusion of study participation. However, if the investigator learns of any SAE/SADE, including a death, at any time after a participant has been discharged from the study, and he/she considers the event to be reasonably related to the study intervention or study participation, the investigator must promptly notify the sponsor.

The method of recording, evaluating, and assessing causality of AEs/ADEs and SAE/SADEs and the procedures for completing and transmitting SAE/SADE reports are provided in [Appendix 2](#).

### **8.6.2. Method of Detecting Adverse Events/Adverse Device Effects and Serious Adverse Events/Serious Adverse Device Effects**

Care will be taken not to introduce bias when detecting AEs/ADEs and/or SAEs/SADEs. Open-ended and non-leading verbal questioning of the participant is the preferred method to inquire about AE/ADE occurrences.

### **8.6.3. Follow-up of Adverse Events/Adverse Device Effects and Serious Adverse Events/Serious Adverse Device Effects**

After the initial AE/ADE/SAE/SADE report, the investigator is required to proactively follow each participant at subsequent visits/contacts. All AEs/ADEs/SAEs/SADEs will be followed until resolution, stabilization, the event is otherwise explained, or the participant is lost to follow-up.

The investigator is obligated to perform or arrange for the conduct of supplemental measurements and/or evaluations as medically indicated or as requested by Allergan to elucidate the nature and/or causality of the AE/ADE or SAE/SADE as fully as possible. This may include additional laboratory tests or investigations, histopathological examinations, or consultation with other health care professionals.

#### Intranasal Tear Neurostimulator

If a participant dies during participation in the study, the investigator will provide Allergan with a copy of any postmortem findings including histopathology.

New or updated information will be recorded in the originally completed CRF.

The investigator will submit any updated SAE/SADE data to Allergan within 24 hours of receipt of the information.

#### **8.6.4. Regulatory Reporting Requirements for Serious Adverse Events/Serious Adverse Device Effects**

- Prompt notification by the investigator to the sponsor of an SAE/SADE is essential so that legal obligations and ethical responsibilities towards the safety of participants and the safety of a study intervention under clinical investigation are met.
- The sponsor has a legal responsibility to notify both the local regulatory authority and other regulatory agencies about the safety of a study intervention under clinical investigation. The sponsor will comply with country-specific regulatory requirements relating to safety reporting to the regulatory authority, IRBs/IECs, and investigators.
- Investigator safety reports must be prepared for suspected unexpected serious adverse reactions according to local regulatory requirements and sponsor policy and forwarded to the investigator as necessary.
- An investigator who receives an investigator safety report describing an SAE/SADE or other specific safety information (eg, summary or listing of SAEs/SADEs) from the sponsor will review and then file it along with the investigator's brochure and will notify the IRB/IEC, if appropriate, according to local requirements.

#### **8.6.5. Pregnancy**

- If a female study participant becomes pregnant, the investigator should inform Allergan within 24 hours of confirming the pregnancy [REDACTED] Best practices are to be followed to ensure the welfare of the participant and the fetus.
- Once the pregnancy has reached term, the second page of the Pregnancy Surveillance Form concerning outcome is to be completed by the investigator and submitted to the sponsor. The sponsor will contact the investigator to obtain information about the pregnancy outcome.

## Intranasal Tear Neurostimulator

- Hospitalization for a normal delivery or elective abortion of a normal fetus does not constitute an SAE. Abnormal pregnancy outcomes (eg, spontaneous abortion, fetal death, stillbirth, congenital anomalies, ectopic pregnancy) are considered serious.

Additional details are provided in [Appendix 6](#).

### **8.6.6. Medical Device Incidents (Including Malfunctions)**

Medical devices are being provided for use in this study for the purposes of evaluating goblet cell degranulation produced by nasal neurostimulation. In order to fulfill regulatory reporting obligations worldwide, the investigator is responsible for the detection and documentation of events meeting the definitions of incident, deficiency, or malfunction that occur during the study with such devices, using the Device Deficiency Form.

The definitions of a medical device incident and a device deficiency can be found in [Appendix 7](#).

Incidents fulfilling the definition of an AE/ADE/SAE/SADE will also follow the processes outlined in Section [8.6.3](#) and [Appendix 2](#) of the protocol.

#### **8.6.6.1. Time Period for Detecting Medical Device Incidents**

- Medical device incidents, deficiencies, or malfunctions of the device that result in an incident will be detected, documented, and reported during all periods of the study in which the medical device is used.
- If the investigator learns of any incident at any time after a participant has been discharged from the study, and such incident is considered reasonably related to a medical device provided for the study, the investigator will promptly notify the sponsor.

The method of documenting medical device incidents is provided in [Appendix 7](#).

#### **8.6.6.2. Follow-up of Medical Device Incidents**

- All medical device incidents involving an AE/SAE will be followed and reported in the same manner as other AEs (see Section [8.6.3](#)). This applies to all participants, including those who discontinue study intervention or the study.
- The investigator is responsible for ensuring that follow-up includes any supplemental investigations as indicated to elucidate the nature and/or causality of the incident.
- New or updated information will be recorded on the originally completed form with all changes signed and dated by the investigator.

#### **8.6.6.3. Prompt Reporting of Medical Device Incidents to Sponsor**

- Medical device incidents will be reported to the sponsor within 24 hours after the investigator determines that the event meets the protocol definition of a medical device incident.

#### Intranasal Tear Neurostimulator

- The Medical Device Incident Report Form will be sent to the sponsor by email. If email is unavailable, then fax should be used.
- The same individual will be the contact for the receipt of medical device reports and SAEs.

#### **8.6.6.4. Regulatory Reporting Requirements for Medical Device Incidents and Deficiencies**

- The investigator will promptly report all incidents occurring with any medical device provided for use in the study in order for the sponsor to fulfill the legal responsibility to notify appropriate regulatory authorities and other entities about certain safety information relating to medical devices being used in clinical studies.

The investigator, or responsible person according to local requirements (eg, the head of the medical institution), will comply with the applicable local regulatory requirements relating to the reporting of incidents to the IRB/IEC.

#### **8.6.7. Adverse Events of Special Interest**

AEs related specifically to impression cytology, including:

- Conjunctival hyperemia
- Chemosis (swelling)
- Discomfort (foreign body sensation, pain)
- Allergic reaction

#### **8.6.8. Medication Errors**

Medication error refers to any unintended error in the dosing and/or administration of the study intervention as per instructions in the protocol. Medication errors generally fall into 4 categories as follows:

- Wrong study intervention
- Wrong dose (including dosing regimen, strength, form, concentration, or amount)
- Wrong route of administration
- Wrong participant (ie, not administered to the intended participant)

#### **8.7. Treatment of Overdose**

Treatment of overdose is not applicable to this ophthalmology device study.

Intranasal Tear Neurostimulator

## 8.8. Pharmacokinetics

Pharmacokinetic parameters are not evaluated in this study.

## 8.9. Pharmacodynamics

Pharmacodynamic parameters are not evaluated in this study.

## 8.11. Health Economics

Health economics are not evaluated in this study.

# 9. Statistical Considerations

## 9.1. Statistical Hypotheses

For the primary effectiveness analysis of mean change in goblet cell degranulation post-intranasal application of the ITN compared to without-intranasal application of the ITN, the null and alternative hypotheses are as follows:

- Null hypothesis: Intranasal application of the ITN is equally effective in improving mucin secretion, as measured by the mean change in goblet cell degranulation, post-ITN application at the Application Visit versus without-ITN application at the Screening Visit.
- Alternative hypothesis: Intranasal application of the ITN is not equally effective in improving mucin secretion, as measured by the mean change in goblet cell degranulation, post-ITN application at the Application Visit versus without-ITN application at the Screening Visit.

## 9.2. Sample Size Determination

Approximately 36 participants are required to apply randomized device and complete the Application Visit, in which 24 participants will be in the intranasal ITN application group and 12 will be in the extranasal ITN application group. Approximately 50 participants may be enrolled to meet this goal.

It is assumed that the standard deviation of the change in goblet cell degranulation post-ITN application versus pre-ITN application is 4.52. With 24 participants in the intranasal ITN application group, it is estimated that the accuracy of a half width of the 95% CI is approximately 1.8.

Intranasal Tear Neurostimulator

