## 4. Study Design

### 4.1. Overall Design

This is a prospective, randomized, controlled, parallel-group, open-label, single-center study in participants with DED.

This study consists of 2 visits: Screening and the Application Visit (Day 0). A study schema is located in Section 1.2 and the Schedule of Visits and Procedures is located in Section 1.3.

Participants will be randomized (in a 2:1 ratio) at Screening to either intranasal or extranasal acute (single) application of the ITN, which they will apply accordingly for approximately 3 minutes during the Application Visit. Approximately 36 participants with DED will be enrolled at a single site in the United States.

At Screening, and prior to any testing, participants will be provided with an IRB-approved ICF which they will have the opportunity to review and ask questions about before written consent is obtained. The Screening Visit should occur 30 to 60 days prior to the Application Visit.

The Application Visit will be separated into pre-ITN application and post-ITN application assessments. CDVA, slit-lamp examination, TMH measurement via OCT, and tear collection will occur at least 45-minutes prior to ITN application, and will be performed again following ITN application. Impression cytology will be performed following these procedures after ITN application.

Safety measures will be assessed before and after ITN application at the Application Visit, including CDVA and slit-lamp biomicroscopy. AEs will be queried prior to study exit.

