## 5. Study Population

The study population will consist of adult male and female participants with objective and subjective evidence of DED. The study will be conducted at a single site and will enroll up to 36 participants who have provided written informed consent and have met the eligibility criteria below.

Prospective approval of protocol deviations to recruitment and enrollment criteria, also known as protocol waivers or exemptions, is not permitted.

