### **6.3. Measures to Minimize Bias: Randomization and Blinding**

At the time of randomization at the Screening Visit, qualified participants will be randomly assigned in a 2:1 ratio to receive either intranasal ITN or extranasal (control) ITN stimulation at the Application Visit. Electronic randomization methods will be used to create a randomization scheme prior to study start.

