## 10.5. Appendix 5: Study Tabular Summary

Parameter Group	Parameter	Value
Trial information	Trial Title	Goblet Cell Degranulation Produced by Nasal Neurostimulation: A Randomized, Controlled Study in Patients with Dry Eye Disease
	Clinical Study Sponsor	Allergan, Inc.
	Trial Phase Classification	Post-market
	Trial Indication	Dry eye disease
	Trial Indication Type	Exploratory
	Trial Type	Efficacy Safety
	Trial Length	1 day, plus the Screening Visit 30 to 60 days prior to Day 0
	Planned Country of Investigational Site	United States
	Planned Number of Participants	36
	FDA-Regulated Device Study	Yes
Participant information	FDA-Regulated Drug Study	No
	Pediatric Study	No
	Diagnosis Group	Dry eye disease
	Healthy Participant Indicator	No
	Planned Minimum Age of Participants	22
	Planned Maximum Age of Participants	N/A
Sex of Participants	Male or female	
	Stable Disease Minimum Duration	Not specified

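### Section 5 caps enrolment at 36 eligible participants, but section 9.2 needs about 36 to complete the Application Visit and allows about 50, so the cap leaves no room for loss after randomization

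*Protocol*

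**What the plan says.** The protocol gives its participant numbers in four places.

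- Section 9.2 defines the target by completion: "Approximately 36 participants are required to apply randomized device and complete the Application Visit", split 24 intranasal and 12 extranasal. It then gives a margin: "Approximately 50 participants may be enrolled to meet this goal". The only stated justification for the size is a 95% CI half-width of about 1.8 for the mean change with 24 intranasal participants and an SD of 4.52.
- Section 5 sets a maximum: the study "will enroll up to 36 participants who have provided written informed consent and have met the eligibility criteria below".
- Section 4.1 says: "Approximately 36 participants with DED will be enrolled at a single site in the United States".
- Appendix 5 lists "Planned Number of Participants" as 36, without saying whether these are enrolled or completing participants.

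On timing, section 6.3 places allocation at the first visit: "At the time of randomization at the Screening Visit, qualified participants will be randomly assigned in a 2:1 ratio". Section 4.1 adds: "The Screening Visit should occur 30 to 60 days prior to the Application Visit". Section 8 dates study entry from randomization, and section 5.4 defines screen failures as people who consent but do not enter. Section 7.2 provides for withdrawal at any time and for discontinuation after use of a prohibited intervention.

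**The concern.** The same word, enrol, carries a ceiling of 36 in section 5 and of about 50 in section 9.2. A site that follows section 5 stops once 36 eligible people are in. A site that follows section 9.2 may go on until about 36 have completed.

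The difference matters because allocation comes a month or two before the intervention. Table 8-1 schedules the second goblet cell measurement at the "Application Visit after randomized ITN application", so a participant lost before Day 0 stays in the ITT population (section 9.3, all randomized) but has no change value. At stake is whether the intranasal group reaches the 24 on which the precision statement rests, and whether the extranasal group reaches its planned 12.

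**Working it through.** **Inputs.** SD of change 4.52; 24 intranasal and 12 extranasal completers; half-width about 1.8; about 50 enrolled (all section 9.2). Cap of 36 eligible (section 5). Ratio 2:1 (section 6.3). Interval of 30 to 60 days (section 4.1). The protocol states no loss rate and no screen-failure rate, so both are varied below as assumptions.

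**Step 1: reproduce the plan's figure.** Half-width = 1.96 × SD / √n = 1.96 × 4.52 / √24 = 1.808. This is the stated 1.8, so the plan used the normal quantile. With the t quantile on 23 degrees of freedom it is 2.0687 × 4.52 / √24 = 1.909.

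**Step 2: reserve under each section.** At 2:1, 36 randomized gives 24 and 12. The target is also 24 and 12, so the reserve under section 5 is 36 − 36 = 0. Section 9.2 has a margin of 50 − 36 = 14, or 28% of 50.

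**Step 3: effect on precision of losing intranasal participants under the cap** (assumed losses, normal-based).

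| Intranasal completers | Half-width | Relative to 24 |
|---|---|---|
| 24 | 1.808 | 1.00 |
| 23 | 1.847 | √(24/23) = 1.02 |
| 22 | 1.889 | √(24/22) = 1.04 |
| 20 | 1.981 | √(24/20) = 1.10 |

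**Step 4: number to randomize for 36 completers.** N = 36 / (1 − d), rounded up, for an assumed loss d.

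| Assumed loss d | N to randomize |
|---|---|
| 5% | 38 |
| 10% | 40 |
| 15% | 43 |
| 20% | 45 |
| 28% | 50 |

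Every one of these exceeds the section 5 cap.

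**Step 5: does the margin of 50 cover this?** That depends on what the 50 counts.

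- If it counts randomized participants, every value in step 4 fits.
- If it counts consented participants, screen failures come out first. Randomizing 42 then requires 42/50 = 84% to pass screening (at most 16% failing), and randomizing 45 requires 90% (at most 10% failing).
- If 28% fail screening, 50 × 0.72 = 36 are randomized and no reserve remains even under section 9.2. Randomizing 42 would then need 42/0.72 = 58.3, so 59 consented.

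**The case against.** The best defence is that the numbers count different people: 50 consented, 36 eligible after screen failures. The protocol does use the term loosely. The study schema puts screening and enrolment together at Visit 1, section 8 numbers everyone who consents, and sections 4.1 and 9.2 both say approximately. This explains much of the gap between 36 and 50. It does not explain how at most 36 eligible participants, randomized at least 30 days before application, become about 36 completers when section 7.2 itself foresees loss.

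The objection that the consequence is small largely stands. One intranasal loss gives 1.847, still about 1.8 when rounded. Appendix 5 classes the trial as exploratory, section 9.4.1.3 reports summary statistics with a 95% CI, and section 9.2 sets no power or success threshold. Losses in the extranasal group touch no stated precision target. The choice between normal and t quantile (1.81 against 1.91) moves the half-width more than two losses do.

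Three stronger readings are tempting and are not supported. A reader might infer that the sample-size calculation fails or allows for no loss at all; but the figure reproduces and section 9.2 contains a margin, so the lack of reserve belongs to section 5 alone. A reader might infer that randomizing, say, 39 to 45 fits within the 50 at no extra cost; step 5 shows that this depends on an undefined count and an unstated screen-failure rate. A reader might infer that no replacement of losses is foreseen; the schedule of activities and the visit descriptions are redacted or not shown, so such a rule may exist. It would still not make 36 and about 50 agree.

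**Conclusion.** The inconsistency is real and rests on text that can be read. Section 5 is the only place with a firm maximum, and that maximum equals the number section 9.2 needs at the end of the study. Followed literally, section 5 reaches 24 and 12 only with zero loss over 30 to 60 days.

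The cost in precision is modest: 2%, 4% and 10% wider intervals for one, two and four intranasal losses. These loss counts are scenarios, because the protocol states no rate. The point should be corrected because it determines when the site stops enrolling and the remedy is simple; it does not undermine the trial. Appendix 5 and section 4.1 are ambiguous more than wrong.

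Separately, and of lesser weight, about 1.8 is slightly favourable as a planning figure for a CI that will use an estimated SD.

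**What to change.** 1. Remove the maximum of 36 from section 5.
2. Align sections 4.1, 5, 9.2 and Appendix 5 so that approximately 36 (24 and 12) is everywhere the number who complete the Application Visit, with enrolment continuing, or losses being replaced, up to the section 9.2 maximum.
3. State whether the approximately 50 counts consented or randomized participants.
4. Let the sponsor choose and state the allowance for loss. Either route in item 2 meets the target. Since application follows Screening by 30 to 60 days, a replacement completes at least 30 days after being screened.
5. Secondary: give the half-width as about 1.9 (t-based, 1.909 with 24 participants and SD 4.52), or label 1.8 as normal-based.

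The cost is wording in four places. If the 50 counts randomized participants, nobody beyond the present allowance is needed at losses of up to 28%. If it counts consented participants, whether the allowance suffices depends on screen failures, and the sponsor may have to raise it or accept a smaller reserve.

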#### **9.4.1.3. Primary Effectiveness Analyses**

The primary effectiveness variable will be the number of goblet cells degranulated in the study eye. The study eye will be the eye with the lower tear meniscus height prior to the application or, if both eyes are equal, the right eye.

The primary effectiveness endpoint will be the mean change in goblet cell degranulation post-intranasal application of the ITN at the Application Visit compared to without-intranasal application of the ITN at the Screening Visit. Summary statistics of count, mean, median, minimum, and maximum will be provided to evaluate the change in the number of degranulated goblet cells and a 95% CI will also be provided.

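### The planned 95% CI half-width of about 1.8 treats the SD as known; with the SD estimated from 24 changes the planning value is about 1.9

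*Protocol*

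**What the plan says.** Protocol Section 9.2 (Sample Size Determination) gives two inputs and one result.

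- The SD: "It is assumed that the standard deviation of the change in goblet cell degranulation post-ITN application versus pre-ITN application is 4.52".
- The group size: "With 24 participants in the intranasal ITN application group".
- The resulting precision: "it is estimated that the accuracy of a half width of the 95% CI is approximately 1.8".

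It names no quantile or formula and does not say whether the SD is taken as known.

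The 24 are completers. The same section says "Approximately 36 participants are required to apply randomized device and complete the Application Visit", splits these into 24 intranasal and 12 extranasal, and adds "Approximately 50 participants may be enrolled to meet this goal". Dropout is therefore already allowed for.

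Section 9.4.1.3 (Primary Effectiveness Analyses) plans summary statistics for the change in the number of degranulated goblet cells and says "a 95% CI will also be provided". It does not name the type of interval. The visible text gives no power, target effect or precision threshold.

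**The concern.** A sample size justified by precision rests on its half-width. Here that is one number, with no power calculation beside it. The number should describe the kind of interval that will be reported: a 95% CI for a mean change whose SD comes from the same 24 participants. The normal quantile gives too narrow an interval in that setting, and always in the same direction. At 24 participants the difference is small, but it is enough to change the one decimal that the protocol reports. What is at stake is the accuracy of the stated precision, not the validity of the trial or the choice of 24.

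**Working it through.** **Inputs.** SD of the change 4.52, intranasal group size 24, two-sided 95% confidence (all Section 9.2). The 2:1 allocation (Section 6.3) does not enter a one-group half-width. No further dropout adjustment applies, because 24 is the number completing.

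**Step 1: standard error.** 4.52/√24 = 4.52/4.899 = 0.9226.

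**Step 2: reproduce the stated figure.** Normal quantile: 1.960 × 0.9226 = 1.808, which rounds to 1.8. The stated figure is reproduced.

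**Step 3: could another formula also give 1.8 at 24 participants?**

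| Calculation | Half-width |
|---|---|
| Two-sided normal quantile | 1.808 |
| Two-sided t, 23 df | 1.909 |
| Expected two-sided t half-width, allowing for sampling of the SD | 1.888 |
| One-sided 95% t, 23 df | 1.58 |
| Between-arm difference, 24 vs 12, SD 4.52 assumed in both arms, normal quantile | 3.13 |
| Same, t with 34 df | 3.25 |

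Of these, only the two-sided normal quantile gives 1.8. That the plan used it is an inference from this arithmetic, since Section 9.2 does not say so.

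**Step 4: SD estimated.** The 97.5% point of t with 23 df is 2.069. Half-width: 2.0687 × 0.9226 = 1.909, about 1.9. Allowing for the sampling of the SD, the expected half-width is 1.888, also about 1.9.

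**Step 5: size of the gap.** 1.909 − 1.808 = 0.10, and 1.909/1.808 = 1.055, so the interval is about 5.5% wider.

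**Step 6: the gap in participants.** t-based half-width at an SD of 4.52:

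| Intranasal completers | Half-width |
|---|---|
| 24 | 1.909 |
| 25 | 1.866 |
| 26 | 1.826 |
| 27 | 1.788 |

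A value that rounds to 1.8 needs 26; one at or below 1.80 needs 27. The gap is therefore two to three participants.

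**Step 7: optional upper bound.** If the true SD is 4.52 and the changes are normal, the realised half-width is 1.909 × √(χ²/23), with χ² on 23 df. The 80th percentile of that χ² is about 28.43, giving 1.909 × √(28.43/23) = 2.12, about 2.1.

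**The case against.** The best defence is that nothing was miscalculated. Section 9.2 says that the SD is assumed and the half-width approximate. With an assumed SD the normal formula is a common planning shortcut, and under it the figure reproduces exactly. No threshold, power or success rule hangs on 1.8, and the numbers of completers and enrolled participants are themselves approximate. All of this stands, and it makes the figure an optimistic approximation rather than a slip in arithmetic. It does not rescue the figure itself: to the one decimal reported, the half-width with an estimated SD is 1.9.

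Three stronger readings are tempting, and the documents do not support them.

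- A reader might infer that the reported interval will cover less than 95%. An interval using 1.96 with an SD estimated on 23 df would cover about 93.8%. But Section 9.4.1.3 names no quantile, and a planning shortcut does not bind the analysis. That harm is hypothetical.
- A reader might note that, with a true SD of 4.52 and normal data, the realised half-width is 1.8 or less only about 39% of the time. Most of that reflects ordinary sampling variation in the SD. Even for 1.9 the corresponding chance is only about 53%, so the 39% does not measure the fault.
- A reader might fault Section 9.4.1.3 for not naming a one-sample t interval. That detail is commonly left to the SAP, which is not at hand, and its absence from the protocol is no finding.

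**Conclusion.** The point holds as a minor one. At an SD of 4.52 and 24 intranasal completers, the planning half-width of a 95% CI with an estimated SD is 1.91, against the stated 1.8. The like-for-like excess is 0.10, or about 5.5%. The plan's only visible quantitative basis for its sample size is slightly too favourable.

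This rests on the protocol's own SD and group size, on the SD being estimated from the trial's data, and on the t interval as the usual interval for a mean change. The value 1.9 is itself a planning value; the realised width will move with the observed SD.

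It would go too far to conclude that 24 participants are too few. The visible text sets no precision requirement that 1.9 would miss.

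**What to change.** In Section 9.2, restate the half-width as approximately 1.9, and say that it is based on the t distribution with 23 df at an SD of 4.52. Leave the sample size unchanged. Optionally add that the half-width will be no more than about 2.1 with 80% probability if the true SD is 4.52 and the changes are normal. No edit to Section 9.4.1.3 is needed.

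The cost is one sentence, or two with the optional bound, and a slightly less favourable figure. Recruitment, conduct and the planned analysis are unaffected.
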